All prescription and over-the-counter medications as well as alternative medicines that have been taken within 4 weeks prior to the first dose of pazopanib must be fully documented in the Case Report Form (CRF; indication, dose information and dates of administration). The Investigator or a designee must be informed as soon as possible about any new medication taken from the time of screening until the end the study; these new medications will be fully documented in the CRF (indication, dose information, and dates of administration).

All concomitant medications taken during the study will be recorded in the CRF with indication, dose information, and dates of administration.

Precautions/Warnings

Certain drugs which induce or inhibit cytochrome P450 enzymes are prohibited. **Medical personnel must refer to the list of prohibited agents in Section 7.4 prior to administering treatment.**

Certain drugs which are listed as “use with caution” should be avoided if possible, but if necessary, subjects who receive these medications should be closely monitored for AEs. **Medical personnel must refer to the list of “use with caution” agents in Section 7.4 prior to administering treatment.**

Hypertension is an important AE associated with pazopanib. Frequent **blood pressure (BP) monitoring is important** in subjects receiving pazopanib versus placebo starting on day 8 and continuing until the subject is off study. Experience to date suggests that increases in BP may occur following dosing with pazopanib for a number of weeks and that these increases may occur relatively quickly. **Section 7.7** includes specific guidelines on the management of treatment-emergent hypertension. Recommendations for hypertension monitoring and management are presented in **Appendix F**.

QTc prolongation and Torsades de Pointes is a rare but serious adverse event associated with pazopanib. Therefore, the following is required:

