- **Intensive QTc monitoring. A baseline ECG is required prior to study registration, and subjects with QTc \geq 480 msec are excluded.** Repeat ECG must be performed during the week 2. After surgery, for those subjects continuing on maintenance pazopanib, if the QTc interval at 4 weeks is \geq 500 msec, the ECG should be repeated within 7 days and, if the QTc interval remains \geq 500 msec, the subject should be removed from the study. Additionally, if the QTc interval is increased by 60 msec or more from baseline but the QTc interval remains at $<$ 500 msec, an ECG should be repeated within 7 days. If the repeat ECG again shows a \geq 60 msec increase in the QTc interval from baseline, consideration should be given to removing the subject from the study or increasing monitoring, after discussion with the Principal Investigator.
- **Subjects must be questioned about family history of prolonged QTc, personal history of prolonged QTc, relevant cardiac disease, and concomitant medications which are associated with a high risk of causing QTc prolongation prior to study registration.**
- **Concomitant treatment with drugs that are associated with a high risk of causing QTc prolongation should be changed to similar agents that do not pose such a risk, if possible, prior to a subject receiving the first dose of pazopanib.** A comprehensive list of agents that are associated with a risk of prolonging the QTc interval is provided in **Appendix E**.
- **Potassium, calcium, phosphate, and magnesium levels must be obtained before administration of the first dose of pazopanib and frequently thereafter (as described in the Study Calendar, Appendix A).**

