- **Abnormalities that occur after enrollment in potassium, calcium, phosphate, and magnesium levels should be managed as follows:** Pazopanib should be held and an ECG must be performed for hypokalemia or hyperkalemia \geq grade 2; hypocalcemia or hypercalcemia \geq grade 3; hypophosphatemia \geq grade 3; hypomagnesemia or hypermagnesemia \geq grade 3. Grading is according to CTCAE v4. These laboratory values should be corrected as soon as possible in a manner consistent with good medical judgment. Pazopanib may be re-administered when hypokalemia or hyperkalemia is grade 1 or within institutional limits; hypocalcemia or hypercalcemia is \leq grade 2, hypophosphatemia is \leq grade 2; and hypomagnesemia or hypermagnesemia is \leq grade 2. Even though pazopanib administration is allowed at these lower grades, every effort should be made to correct the abnormal lab values to normal if possible.

If an ECG, obtained because of these lab values, reveals an increase in the QTc to >500 msec or an increase in the QTc by at least 60 msec from baseline, the ECG should be repeated before re-administration of pazopanib. If the QTc interval, on the repeat ECG, is still ≥ 500 msec, the subject should be removed from the study. If the QTc, on the repeat ECG, remains increased in the QTc by at least 60 msec from baseline but is less than 500 msec, consideration should be given to removing the subject from the study.

Renal function (creatinine and urinary protein) should be frequently monitored as suggested by the pathologic changes noted in animal studies and evidence from studies of other antiangiogenic agents. Specific guidelines for management of proteinuria and elevated creatinine are presented in **Section 7.7**.

Hepatic Function monitoring include ALT, AST, GGT, alkaline phosphatase and total bilirubin at the following visits:

- at screening;
- before initiation of pazopanib treatment;
- end of week 2;
- prior to Day 1 of each cycle;
- at post-treatment visit;
- final visit;
- 30-day follow-up

Periodic monitoring should continue monthly if pazopanib monotherapy is continued. Pazopanib is not recommended for subjects with severe hepatic impairment (defined as $>3 \times$ ULN, regardless of any level of ALT).

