7.7.1 Dose Interruptions/Modifications for Specific, Non-liver Related, Toxicities

Recommendations for pazopanib (investigational product, IP) dose interruptions/modifications in case of specific treatment-emergent AEs are provided in Table 1.

Table 1 Dose Modification Algorithms for Potential Treatment-Related Adverse Events

AE Terms & Descriptions	Dose Modification Algorithms
-------------------------	------------------------------

AE Terms & Descriptions	Dose Modification Algorithms
Hypertension	
(A). Asymptomatic and persistent SBP of ≥ 140 and < 170 mmHg, or DBP ≥ 90 and < 110 mmHg, or a clinically significant increase in DBP of 20 mmHg (but still below 110 mmHg).	
Step 1. Continue investigational product (IP) at the current dose.
 
Step 2. Adjust current or initiate new antihypertensive medication(s).
 
Step 3. Titrate antihypertensive medication(s) during next 2 weeks as indicated to achieve well-controlled^a blood pressure (BP). If BP is not well-controlled within 2 weeks, consider referral to a specialist and go to scenario (B).

(B). Asymptomatic SBP ≥ 170 mmHg, or DBP ≥ 110 mmHg, or failure to achieve well-controlled BP within 2 weeks in scenario (A).	
Step 1. Consider reducing or interrupting IP, as clinically indicated.
 
Step 2. Adjust current or initiate new antihypertensive medication(s).
 
Step 3. Titrate antihypertensive medication(s) during next 2 weeks as indicated to achieve well-controlled BP.
 
Step 4. Once BP is well-controlled, restart IP dose-reduced by 200 mg if IP was interrupted.

(C). Symptomatic hypertension or recurring SBP ≥ 170 mmHg, or DBP ≥ 110 mmHg, despite modification of antihypertensive medication(s)	
Step 1. Interrupt IP
 
Step 2. Adjust current or initiate new antihypertensive medication(s).
 
Step 3. Titrate antihypertensive medication(s) during next 2 weeks as indicated to achieve well-controlled BP. Referral to a specialist for further evaluation and follow-up is also recommended.
 
Step 4. Once BP is well-controlled, restart IP dose-reduced by 200 mg.

(D). Refractory hypertension unresponsive to above interventions.	Discontinue IP and continue follow-up per protocol.
Prolongation of QTc Interval: If the QTc is prolonged, the ECG should be manually read to ensure accuracy of the reading. The values below refer to manually-read ECGs. Refer to Section 7.1.1 for ECG monitoring	
QTc $\geq 480 < 500$ msec	Continue IP; monitor as clinically indicated.

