QTc ≥ 500 msec	Discontinue IP and continue follow-up per protocol.
Proteinuria	
UPC <3	Continue pazopanib at the current dose; monitor as clinically indicated
UPC ≥ 3 or 24-h urine protein ≥ 3 g	
Step 1. Interrupt IP.
 
Step 2. Weekly UPC or 24-hr urine protein monitoring until UPC is <3 or 24-hr urine protein is <3 grams. Then restart pazopanib dose-reduced by 200 mg.
 
Step 3. If UPC ≥ 3 or 24-h urine protein ≥ 3g recurs, repeat steps 1 and 2.
 
Step 4. If UPC ≥ 3 or 24-hr urine protein ≥ 3g recurs and the pazopanib dose can no longer be reduced, discontinue pazopanib and continue follow-up per protocol.

Hemorrhage /Bleeding: Investigate and document underlying etiology of the bleeding	
Grade 1	For hemoptysis, interrupt pazopanib and contact the Novartis Study Physician to discuss whether further treatment with pazopanib is appropriate.

	For other Grade I hemorrhage/bleeding events, continue pazopanib at the current dose; monitor as clinically indicated.
Grade 2	Step 1. If pulmonary or GI bleed (other than hemorrhoidal bleeding), discontinue IP and continue follow-up per protocol. Otherwise, interrupt IP until the AE resolved to \leq Grade 1. Step 2. Restart IP; consider reducing dose and monitor as clinically indicated.
Grade 3 or 4, or Recurrent \geq Grade 2 event after dose interruption/reduction.	Discontinue IP and continue with follow-up per protocol.
Venous Thrombosis (DVT, PE)	
Grade 2	Continue IP at the current dose; monitor as clinically indicated
Grade 3	Step 1. Interrupt IP. Step 2. Initiate and monitor anticoagulation as clinically indicated. Step 3. Resume IP at same dose only if all of the following criteria are met: 
 • The subject must have been treated with anticoagulant at the desired level of anticoagulation for at least one week. • No Grade 3 or 4 or clinically significant Grade 2, hemorrhagic events have occurred while on anticoagulation treatment. Subject should be monitored as clinically indicated during anticoagulation treatment and after resuming study treatment. When treating with warfarin, international normalized ratio (INR) should be monitored within three to five days after any change in IP dosing (eg, re-initiating, escalating/de-escalating, or discontinuing IP), and then at least weekly until the INR is stable. The dose of warfarin (or its derivatives) may need to be adjusted to maintain the desired level of anticoagulation

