7.8 Criteria for Evaluability and Removal/Withdrawal from Treatment

Criteria for evaluability of the Trial

- Patients must have received a total of at least 80% of the intended dose of doxorubicin, ifosfamide, and pazopanib to be evaluable for the trial. If less than this amount is received, the patient may remain on the study, but will not be evaluated for primary endpoints.

Criteria for stopping therapy:

- Substantial non-compliance with the requirements of the study.
- Any adverse event which, in the Investigator's opinion, requires termination of the study medication.
- Disease progression, unless at the discretion of the Investigator (in collaboration with Novartis) continued treatment with study drug is appropriate.
- The patient would benefit from additional radiation therapy beyond that specified in the protocol.
- Request by the patient or a legal representative/relative to stop the treatment.
- The patient presents with a beta-HCG test consistent with pregnancy. Pregnancy will be reported along the same timelines as a serious adverse event.
- The patient uses illicit drugs or other substances that may, in the opinion of the Investigator, have a reasonable chance of contributing to toxicity or otherwise interfering with results.
- The development of a second malignancy that requires treatment, which would interfere with this study.
- The patient is lost to follow-up.
- Interruption in administration of pazopanib or chemotherapy for greater than 3-week delay.
- Development of an intercurrent illness or situation which would, in the judgment of the Investigator, affect assessments of clinical status and study endpoints to a significant degree.

Criteria for study withdrawal:

- Study closure.
- Patient decision to withdraw from both study therapy and follow-up.

The Investigator will make every reasonable effort to keep each patient in the study unless it is in the patient's best interest to discontinue participation. If a patient is removed from the study or declines further participation, all End of Treatment evaluations should be performed if the patient is willing and able to be assessed. A description of the reason(s) for withdrawal from the study will be recorded on the case report form (CRF). The Investigator should also ensure that all patients are followed up for survival and recurrence after the Final Visit.

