Relevant visit data should be entered on the CRF and any unused study medication will be accounted for and returned for all patients participating in the study, even for a brief period of time. Patients who discontinue following entry will have relevant information completed and recorded on the CRF. All patients who discontinue because of adverse events or clinically significant laboratory abnormalities should be followed up until they recover or stabilize, and the subsequent outcome will be recorded. If any patient should die during the trial or within 30 days of stopping study treatment, the Investigator will inform the IRB and the Novartis representative. The cause of death should be recorded in detail, within 24 hours, on a serious adverse event (SAE) form and reported to the IRB and Novartis.

Subjects who are withdrawn from the study prior to surgery will be replaced and randomized to treatment with pazopanib versus placebo according to the 2:1 design.

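### For a QTc of 500 msec or more on pazopanib, Section 7.1.1 and Table 1 of Section 7.7.1 give different instructions, and the 4-week maintenance rule states no hold while the repeat ECG is awaited

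*Combined protocol and SAP*

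**What the plan says.** Section 7.1.1 (Precautions/Warnings) introduces its ECG rules with the statement that "QTc prolongation and Torsades de Pointes is a rare but serious adverse event associated with pazopanib" and presents them as required. Two of them deal with a QTc around 500 msec.

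- **Maintenance rule.** After surgery, for patients continuing on pazopanib, if the 4-week QTc is 500 msec or more, "the ECG should be repeated within 7 days and, if the QTc interval remains" at or above 500 msec, the patient is to be removed from the study. The bullet does not say whether dosing continues or stops before the repeat.
- **Electrolyte rule.** For listed potassium, calcium, phosphate and magnesium abnormalities, pazopanib is held and an ECG is done. If the QTc is above 500 msec or has risen by at least 60 msec, "the ECG should be repeated before re-administration of pazopanib". If the QTc on the repeat "is still ≥ 500 msec, the subject should be removed from the study".

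Table 1 in Section 7.7.1 has its own QTc block. Its heading asks for a manual reading to check accuracy and adds: "The values below refer to manually-read ECGs. Refer to Section 7.1.1 for ECG monitoring". The action for 500 msec or more is "Discontinue IP and continue follow-up per protocol". It names no repeat ECG and no persistence condition.

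Section 7.8 lists criteria for stopping therapy separately from criteria for study withdrawal. The withdrawal list has two entries: study closure and "Patient decision to withdraw from both study therapy and follow-up". The same section asks that all patients be followed for survival and recurrence.

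**The concern.** The same ECG reading leads to different actions depending on which section a site opens, and no text says which governs. Section 7.1.1 is framed as required and Section 7.7.1 as recommendations, so a site could reasonably give 7.1.1 priority. At the 4-week maintenance ECG that would favour the less protective rule.

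Two things are at stake. The first is exposure: whether a maintenance patient with a QTc of 500 msec or more keeps taking, for up to a week, a drug the protocol links to Torsades de Pointes. The second is status: whether such a patient leaves the study or only stops the drug. Section 7.8 treats these as different events, and a toxicity finding is not on its withdrawal list.

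**Working it through.** The check is mainly a comparison of texts; the plan states no figure to reproduce.

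**Step 1: the rules side by side.**

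| | 7.1.1, 4-week maintenance ECG | 7.1.1, electrolyte-triggered ECG | 7.7.1, Table 1 |
|---|---|---|---|
| First trigger | QTc ≥500 | QTc >500, or rise ≥60 msec | QTc ≥500, manually read |
| Drug before repeat | Not stated | Already held | Discontinued |
| Repeat ECG | Within 7 days | Before re-administration | None named |
| Repeat below 500 | No mandatory removal | Restart left open | No restart provision |
| Repeat still ≥500 | Removed from study | Removed from study | Not applicable |
| Study status | Out | Out | Follow-up continues |

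**Step 2: one reading through both texts.** Take a manually read 505 msec at week 4 of maintenance. Under 7.1.1 the ECG is repeated within 7 days, and removal is mandatory only if the value stays at 500 or above. Under Table 1 pazopanib stops on the 505 reading. If the repeat is 490, 7.1.1 requires no removal; under Table 1 the drug has already been discontinued.

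**Step 3: does the cross-reference settle it?** Table 1 points to 7.1.1 for ECG monitoring. It does not make the drug action depend on 7.1.1, and the accuracy check in its own heading is a manual reading, which is not a second ECG. A confirm-then-discontinue reading is possible but is not written.

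**Step 4: size of the dosing gap in the maintenance rule.**
- Inputs: repeat interval of up to 7 days (7.1.1); 800 mg once daily (7.1.1).
- Doses not excluded under 7.1.1: 7 days × 1 per day = 7.
- Amount: 7 × 800 mg = 5,600 mg.
- Under Table 1: 0.

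**Step 5: size of the gap in the electrolyte rule.** Pazopanib is already held, so no dose is taken while the repeat is awaited. The dosing difference is only whether a repeat below 500 msec can lead to restart (7.1.1) or the stop is permanent (Table 1).

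**Step 6: scope.** The 7.1.1 repeat rules cover only these two situations. For the week-2 run-in ECG, and for the 3-monthly follow-up ECGs in Appendix A, Table 1 alone gives an action at 500 msec or more, unless the ECG was prompted by electrolytes. The same value is therefore handled differently at week 4 and at month 3 of maintenance, with no reason given.

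**The case against.** The strongest reply is that the sections divide the work: 7.1.1 sets ECG timing and Table 1 sets the drug action. A clinician can stop pazopanib on the first reading, repeat the ECG within 7 days, and comply with both. Section 7.1.1 never tells anyone to keep dosing. This stands in part. The 7 doses are permitted by silence, not instructed, and a reader who infers that the protocol orders continued treatment goes beyond the text. The silence still matters, because the electrolyte rule in the same section states its hold and the 4-week rule does not. The reply also leaves the two end actions unreconciled.

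A second reply is that a specific rule for a correctable electrolyte cause can sensibly sit beside a general row. That is a plausible design, but no text adopts it.

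A third concerns run-in. A reader might infer that removal from the study costs the primary analysis patients, since Section 14.1 expects to exclude those withdrawn for toxicity. The documents do not support a material loss:
- Only the electrolyte rule reaches run-in; the 4-week rule applies after surgery.
- Sections 7.8 and 11.0 require 80% of the intended pazopanib dose for evaluability. Since 0.80 × 14 = 11.2, a patient stopped after 11 or fewer full daily doses is not evaluable for the primary endpoints under either text.
- Section 7.8 provides that "Subjects who are withdrawn from the study prior to surgery will be replaced and randomized to treatment with pazopanib versus placebo".

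Nor can loss of survival or recurrence follow-up be inferred, because Section 7.8 asks for it in all patients.

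**Conclusion.** The inconsistency is real and in the current text. At the 4-week maintenance ECG, up to 7 further daily doses (5,600 mg at 800 mg) are not excluded after a QTc of 500 msec or more, against none under Table 1. That figure assumes full dose, a repeat on the last permitted day, and a site that reads the missing hold as leave to continue. For electrolyte-triggered ECGs the dosing difference is restart against permanent stop. In both situations the end action differs: removal from the study against discontinuation with follow-up.

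This is a safety harmonisation for an event that should be infrequent: the trial plans 21 patients randomised 2:1, about 14 on pazopanib (21 × 2/3), and only run-in responders may take maintenance. The documents give no rate of QTc at or above 500 msec, so no event probability is claimed. No run-in loss to the primary endpoint is claimed either, and no stated statistical figure changes.

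**What to change.** Make three edits.

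1. **Section 7.1.1, 4-week rule.** Hold pazopanib from the first manually read QTc of 500 msec or more until the repeat ECG. If the repeat is still 500 msec or more, discontinue it permanently.
2. **Section 7.1.1, both rules.** Where a QTc of 500 msec or more now leads to removal from the study, use Table 1's wording: "Discontinue IP and continue follow-up per protocol".
3. **Table 1, row for 500 msec or more.** State that pazopanib stops at the first manually read value, and that restart is barred unless the investigators explicitly adopt the 7.1.1 exception for a repeat below 500 msec. Whether to adopt it is their clinical decision, but it has to be written down.

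The cost is two or three sentences in 7.1.1 and a phrase in Table 1. If the exception is adopted, a patient whose first reading is not confirmed misses up to about 7 maintenance doses; the manual reading already required limits how often that happens. If it is not adopted, the stop is permanent, as Table 1 already has it.

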7.1.2 Chemotherapy Administration

Pre-operative chemotherapy will consist of doxorubicin and ifosfamide administered on an inpatient basis. Subjects may also receive 2 to 4 cycles of post-operative chemotherapy, (up to 6 cycles total of neoadjuvant plus adjuvant chemotherapy).

Doxorubicin: 75 mg/m² by continuous IV infusion days 1 through 3 of each cycle.

Ifosfamide: 2.0 g/m² over 4 hours IV, days 1 through 5 of each cycle.

Mesna: 400 mg/m² IV pre, 4 hours post, and 8 hours post each dose of ifosfamide.

Hydration: D5W with 100 meq/L sodium acetate, 20 meq/L potassium acetate, 4 meq/L magnesium sulfate continuous IV infusion at a rate of 83 mL/hour, begun approximately 2 hours prior to chemotherapy and discontinued after completion of chemotherapy and Mesna.

Cycle 1 of chemotherapy may only commence after a minimum 6-day washout period of pazopanib.

7.2 Radiation Therapy

Radiation treatment (XRT) will be administered using standard of care delivery and quality assurance techniques, using mega-voltage photons. Electrons may be used if dosimetrically appropriate, but no other particle therapy such as neutrons or protons may be used. Brachytherapy and IORT may be used for boost volumes to sites of residual disease, when appropriate. Simulation must be CT-based, using contrast if possible, and appropriate immobilization devices. Target delineation for preoperative XRT must include the GTV, CTV, PTV and organs at risk, with identified dose constraints, and for postoperative XRT, delineation must include the pre-operative GTV, CTV (i.e., surgical bed), PTV and organs at risk, also with identified dose constraints. Treatment planning must generate dosimetry with no more than plus or minus 5% heterogeneity, while sparing an adequate strip of circumferential tissue to allow ongoing lymphatic drainage, and utilizing external beam delivery techniques, such as IMRT and 3-D conformal approaches when necessary, to achieve this aim. The use of bolus is at the discretion of the radiation oncologist, but is rarely indicated in the preoperative setting.

For preoperative XRT, the prescribed dose to the PTV should be 50 Gy in 25 fractions of 2 Gy/fraction over 5 weeks. If the target volume encompasses sensitive structures such as bowel or lung, the dose can be reduced to 45 Gy in 25 fractions of 1.8 Gy without protocol violation.

For postoperative XRT, the prescribed dose to the PTV should be 50 Gy in 25 fractions of 2 Gy/fraction over 5 weeks, followed by 10 Gy boost (in 5 fractions) to a reduced volume. For contaminated or close margins, the boost dose will be 10 - 16 Gy; for microscopically positive margins, 16 - 20 Gy, and for grossly positive margins, 20- 26 Gy.

Verification must include initial and weekly isocenter imaging checks with image guidance with cone beam CT as appropriate to the technique, as well as weekly on-treatment patient review visits. Diode checks and physics review must be completed as standard procedure.

Maintenance pazopanib for those who respond to therapy during the Run-in period, may not commence until one week following completion of radiation.

